Endocrowns are considered as effective restorations for molars that have undergone endodontic treatment offering better fracture resistance and stress distribution, offer excellent strength for cuspal overlays, it can be used as a final restoration for primary molars preserve tooth structure, and maintain periodontal health⁽¹³⁾.

Up to our knowledge, there is no study evaluate the clinical performance, bacterial adherence, assessment of dental plaque and gingival status of endocrowns and Bioflex crowns as a new restorative modality in Pulpotomized primary molars compared with prefabricated ZCs, and the parental satisfaction toward the three restorations at the end of the 12 month follow-up

Aim of the study

This study will be conducted to evaluate clinical performance, parent's satisfaction, gingival health and bacterial effects of Bioflex crowns & Endocrowns compared to ready-made zirconia Crowns on Pulpotomized primary molars

Patients and Methods

Study Design:

This study will be designed as a randomized clinical trial

Sample Size calculation: ^(7,13)

This study will be conducted to evaluate Clinical performance, bacterial adherence, assessment of gingival health and patient satisfaction of LS2 endocrowns and Bioflex crowns compared with prefabricated zirconia

crowns as a restoration of Pulpotomized primary molars. Assuming there is no difference between groups (equivalence trial), if there is truly no difference between the standard and experimental treatments, then 22 patients in each group are required to be 80% sure that the limits of a two-sided 95% confidence interval will exclude a difference in means of more than 0.6. This number is to be increased to 24 in each group to compensate for possible losses during follow up. Sample size was calculated by sealed envelope power calculator.

Study Setting and Population:

This study will involve children with 72 primary molars who require Pulpotomy treatment at the Pedodontics and Oral Health Department, Faculty of Dental Medicine (Boys, Cairo), Al-Azhar University.

Subject grouping:

The involved primary molars (n= 72) will be divided randomly into 3 groups (n=24) according to the type of the final restoration for Pulpotomized molars as the following

- **Group A:** will be restored with endocrown (study group)
- **Group B:** will be restored with prefabricated Bioflex crown (study group).
- **Group C:** will be restored with prefabricated zirconia crown (control group).

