- Abrasive rubber tip will be used to smoothening and rounding the internal angles giving a polished and smoothed preparation.
- Endocrown will be manufactured using CAD/CAM technology
- internal wall of crown will be treated with etchant material, rinsed, dried then silane coupling agent

- Dual-cure resin cement will be applied on the crown fitting surface for endocrown cementation.

Group B: Preformed Bioflex crowns ⁽¹⁰⁾

According to manufacturer instruction the preparation will be as the follow:

- Light -cured glass ionomer filling of adequate thickness will be applied over the ZOE to seal the cavity before preparation
- A digital caliper will be used to measure a mesio-distal dimension of tooth then suitable sized preformed crown will be selected.
- Tooth preparation will be carried out with a tapered diamond bur for occlusal reduction by 1–1.5 mm, including the central groove.
- The proximal preparation will be around 0.5 mm to clear the contact area
- Placement of the crown will be achieved by a snug fit followed by contouring using a Hover's plier.
- Crown cementation will be carried out using glass ionomer cement and removal of excess cement using floss or explorer.

Group C: performed zirconia crowns ^(10, 12, 13)

- Light -cured glass ionomer filling of adequate thickness will be applied over the ZOE to seal the cavity before preparation.
- A digital caliper will be used to measure a mesio-distal dimension of tooth then suitable sized preformed crown will be selected.

- A diamond bur will reduce the occlusal surface by 1.5–2 mm
- Interproximal contacts will be prepared with a tapered fissure bur. About 1–2 mm sub gingival preparation will be performed
- The selected crown will be placed and checked.
- The passive fit of the crown will be assessed and will be luted with glass ionomer cement.
- Consistent firm finger pressure will be applied during cementation.

Observations:

Clinical Performance Assessment ^(10,12)

- Retention, marginal adaption, fracture of the restoration were scored using a modified United States Public Health Service (USPHS) criterion.
- Dental plaque accumulation and gingival condition were assessed using plaque index (PI) and GI.
- Preparation time and cementation assessment using stop watch to record time from preparation start till final restoration cementation.⁽¹⁵⁾

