- Clinical performance and oral status will be assessed at follow-up periods of 3 (T1), 6 (T2), and 12 (T3) months. At the end of the follow-up (T3), parent's satisfaction analysis toward the color, shape, and size of three restorations will be adopted to directly evaluate their satisfaction toward their children's restorations. Parents' responses were rated on a 5-point Likert-type scale.

Microbiological analysis: ⁽⁹⁾

- The swabs will be collected before preparation of crowns, 3 months, 6 months and 12 months after cementation.
- The number of Streptococcus Mutans, lactobacillus will be digitally counted.
- Swabs will be taken from occlusal surface by means of the tips of sterile cotton
- All specimens were transported immediately to microbiological lab.
- Swabs will be taken from occlusal surface by means of the tips of sterile cotton.
- Samples will be preserved in a transporting medium tube containing 9ml thioglycolate broth medium.
- The number of Streptococcus Mutans, lactobacillus will be digitally counted.

Data Management and Analysis

Data will be analyzed using IBM SPSS advanced statistics (Statistical Package for Social Sciences), version 27 (SPSS Inc., Chicago, IL). Numerical data will be described as mean and standard deviation or median and range. Data will be explored for normality using Kolmogorov-Smirnov test and Shapiro-Wilk test. Comparisons between 3 groups for normally distributed numeric variables will be done using the ANOVA while for non-normally distributed numeric variables will be done by Kruskal Wallis test. An equivalence limit will be checked in the difference between groups. Categorical data will be described as numbers and percentages and comparisons will be done by chi square test or fisher exact as appropriate. A p-value less than or equal to 0.05 will be considered statistically significant. All tests will be two tailed.

References

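### The trial is sized for equivalence on a 95% confidence interval and a 0.6 limit, but the analysis section names only difference tests and leaves the outcome, the visit and the one-or-both-crowns rule open

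*Combined protocol and SAP*

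**What the plan says.** The Sample Size calculation section sets the design basis: "Assuming there is no difference between groups (equivalence trial". It asks for 22 patients per group, raised to 24 for losses, so as to be 80% sure that "the limits of a two-sided 95% confidence interval will exclude a difference in means of more than 0.6". It gives no outcome, visit or standard deviation for the 0.6. Under Subject grouping, endocrown (A) and Bioflex (B) are study groups, and Group C "will be restored with prefabricated zirconia crown (control group".

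The Observations section lists several numeric or scored measures. "Dental plaque accumulation and gingival condition were assessed using plaque index (PI) and GI"; operative time is taken "using stop watch to record time from preparation start till final restoration cementation"; parents' "responses were rated on a 5-point Likert-type scale"; and two bacterial species are counted. On timing, "Clinical performance and oral status will be assessed at follow-up periods of 3 (T1), 6 (T2), and 12 (T3) months".

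The Data Management and Analysis section compares the three groups by ANOVA or Kruskal-Wallis, depending on normality, and categorical data by chi-square or Fisher exact, with a two-tailed 0.05 criterion. On equivalence it says only "An equivalence limit will be checked in the difference between groups".

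**The concern.** A test for a difference asks whether the data contradict equality. An equivalence design asks whether the data rule out a difference larger than a stated limit. A non-significant ANOVA may reflect close agreement or merely wide intervals, so it cannot by itself show that either new crown is equivalent to zirconia. If the analysis section were followed as written, the question the trial was sized for would rest on one sentence that restates neither the 0.6 limit nor the interval rule.

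Two things are at stake. A p-value above 0.05 could be reported as equivalence. And because several outcomes are measured at three follow-up visits and none is designated, the outcome and visit for the equivalence check, and the number of crowns that must pass, could be chosen once results are known.

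**Working it through.** **1. What carries over from design to analysis.**

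| Element | Sample size / grouping text | Analysis section |
|---|---|---|
| Limit | 0.6, difference in means | mentioned, no value |
| Interval | two-sided 95% | not stated |
| Contrasts | inferable: A−C and B−C | differences between groups, unnamed |
| Pass rule | inferable: interval excludes more than 0.6 | not stated |
| Outcome for 0.6 | not named | not named |
| Visit | not named | not named |
| One or both crowns | not stated | not stated |

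The last three rows are empty throughout the document.

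**2. The plan's 22 per group.** Inputs from the Sample Size calculation: limit 0.6, two-sided 95% interval, 80% power, true difference 0. The SD is missing, so 22 cannot be reproduced from the stated inputs alone; one can only ask which SD is consistent with it.

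- Beta split over the two sides: n = 2(1.960 + 1.282)² × SD²/0.6². At SD 0.600 this is 21.01, which rounds up to 22. It reaches 22.0 at SD 0.614. So 22 implies SD 0.600–0.614.
- Beta not split: n = 2(1.960 + 0.842)² × SD²/0.6². At SD 0.694 this is 21.0 and at SD 0.710 it is 22.0. So 22 implies SD 0.694–0.710.

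The document does not say which formula its calculator used.

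**3. Power of the interval rule when all three crowns are truly equal.** By simulation, with normal data, independent molars, 22 per group, and t-based 95% intervals that must lie wholly within ±0.6. The ranges span the SD range and the choice of two-sample or three-group pooled SD.

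| Assumed SD | Each crown | Both crowns |
|---|---|---|
| 0.600–0.614 | 77–81% | 63–68% |
| 0.694–0.710 | 56–61% | 35–41% |

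**4. What a non-significant ANOVA would tell us.** Same set-up, SD 0.600–0.614. In the second and third rows the other new crown equals zirconia.

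| Truth | ANOVA p>0.05 | Interval rule met |
|---|---|---|
| All crowns equal | 95% | 63–68% (both crowns) |
| One crown off by 0.3 | 63–65% | 27–30% (both crowns) |
| One crown off by exactly 0.6 | 7–8% | 2.5% (that crown) |

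A true difference of 0.3 is inside the limit, so the second row does not show false claims of equivalence. It shows how often p>0.05 would be read as equivalence when the evidence the design asks for is absent. The third row is the false-claim case: the ANOVA reading passes about three times as often as the interval rule.

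**5. False-claim rate if each crown is judged separately.** With both new crowns at the limit, the chance that at least one passes is about 4.5% if both lie on the same side of zirconia and 5.0% if they lie on opposite sides. For one crown it is 2.5%.

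**The case against.** The strongest reply is that equivalence is not absent from the analysis section, and that this is a single combined document. The sample-size text gives the limit, the interval and the criterion, and the grouping text labels two study groups and a control. A reasonable reader would take A−C and B−C, each with a 95% interval inside ±0.6. That stands, and the point is limited accordingly. It does not supply the outcome, the visit or the one-or-both rule.

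Several stronger readings are tempting and are not supported:

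- *That equivalence is the trial's stated aim.* The title and the Aim of the study speak of evaluating the crowns compared with zirconia. Equivalence is the basis of the sample size.
- *That 0.6 is wrongly applied to every outcome.* Nowhere does the document apply it to all of them. It simply does not say which one it belongs to.
- *That choosing after the data gives a known inflation.* If a crown sits exactly at the limit on plaque and gingival indices at all three visits, picking the best of six gives a false claim in 7–14% of trials (within-molar correlation 0.8 to 0), against 2.5%. This borrows the 0.6 and a back-solved SD for indices to which the document does not attach them, and the upper end needs uncorrelated visits. It shows the direction of the risk, not its size here.
- *That the trial is underpowered by a definite amount.* The SD is unstated, and the two formulas give very different answers.

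Chi-square and Fisher tests are also unobjectionable for the categorical outcomes, which a limit on a mean difference does not cover.

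**Conclusion.** The concern holds in this limited form and must be fixed. The comparison tests named in the analysis section cannot answer the question for which the trial was sized, and the one sentence on equivalence does not fill the gap. The contrasts and interval rule are inferable; the outcome, the visit and the number of crowns that must pass are not.

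This conclusion follows from the text and needs no assumed SD. The figures illustrating its consequences do: they assume normal data, independent molars, 22 evaluable per group and an SD back-solved from the sample size. The gap between a non-significant ANOVA and demonstrated equivalence is large under the smaller of the two SD ranges (63–65% against 27–30% with one crown off by 0.3).

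**What to change.** In the Data Management and Analysis section, before any data are analysed:

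1. Name the one numeric outcome and the one visit to which 0.6 applies.
2. Make the primary analysis two contrasts, endocrown minus zirconia and Bioflex minus zirconia, each with a two-sided 95% confidence interval for the difference in means, by one method fixed in advance.
3. Declare a crown equivalent only if its whole interval lies between −0.6 and +0.6.
4. State whether each crown is judged separately or both must pass, give the SD used, and restate the power for that choice. No power figure should be written in until that SD is given.
5. For the primary outcome, treat ANOVA or Kruskal-Wallis as supportive, and state that p>0.05 is not evidence of equivalence. Chi-square and Fisher tests may stay for categorical outcomes as difference tests.

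The cost is analysis wording, one sponsor decision and two intervals, with no new data. There are two downsides. The restated power may be less favourable than 80%, particularly if both crowns must pass. If the crowns are judged separately, the chance of at least one false equivalence claim can approach 5%, and the plan should say so.

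### The aim compares each new crown with zirconia, but the planned three-group tests name no contrast with zirconia and can be significant because the two new crowns differ from each other

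*Combined protocol and SAP*

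**What the plan says.** The Aim of the study section sets the comparison as "Bioflex crowns & Endocrowns compared to ready-made zirconia Crowns on Pulpotomized primary molars". Under Subject grouping, 72 molars "will be divided randomly into 3 groups (n=24) according to the type of the final restoration for Pulpotomized molars". Groups A (endocrown) and B (Bioflex) are labelled study groups, and group C "will be restored with prefabricated zirconia crown (control group"). That gives two questions: A against C, and B against C.

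Data Management and Analysis specifies the difference tests by outcome type:
- Normal numeric outcomes: "Comparisons between 3 groups for normally distributed numeric variables will be done using the ANOVA".
- Other numeric outcomes: "for non-normally distributed numeric variables will be done by Kruskal Wallis test".
- Categorical outcomes: "Categorical data will be described as numbers and percentages and comparisons will be done by chi square test or fisher exact as appropriate".

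The threshold is p ≤ 0.05, two-tailed. The only other between-group statement is "An equivalence limit will be checked in the difference between groups", which gives no pair, outcome, limit or confidence level. No post-hoc test, contrast with control or multiplicity adjustment appears anywhere in the document.

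**The concern.** ANOVA and Kruskal-Wallis across three arms ask whether any of the arms differ. One way for that to be true is that endocrown and Bioflex differ from each other, which the aim does not ask. A significant result therefore cannot by itself be read as a statement about either new crown against zirconia, and the plan does not say how to get from one to the other. The investigator would have to choose the follow-up comparisons, and any adjustment, after seeing the data.

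At stake is whether the reported p-values answer the trial's question. A reader could take a positive three-group result as evidence that a new crown is better or worse than the control when the data do not show that.

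**Working it through.** **Inputs from the document.** Three arms, 24 molars each, 22 per arm after the loss allowance; two-sided alpha 0.05; zirconia as control.

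**Inputs that are assumed.** Normal data with a common SD, and the effect sizes below, in SD units relative to zirconia. The document gives no expected effects and no SD.

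**The plan's own figure.** For equivalence of two means with a true difference of 0, n = 2 × [SD × (z₀.₉₇₅ + z₀.₉₀) / 0.6]². The SD is not stated, so 22 cannot be reproduced from stated inputs alone. With an assumed SD of 0.60, n = 2 × (1.960 + 1.282)² = 21.01, rounded up to 22; any SD from 0.600 to 0.614 gives 22. Then 22 / (1 − 0.083) = 24, and 3 × 24 = 72. The point below does not depend on this SD.

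**Step 1: what the omnibus F responds to.** Its power depends on λ = n × Σ(μᵢ − μ̄)², with 2 and 63 df.
- Endocrown +0.4, Bioflex −0.4, zirconia 0: μ̄ = 0, so λ = 22 × (0.16 + 0.16 + 0) = 7.04 and power is 64%.
- Endocrown +0.8, Bioflex +0.4, zirconia 0: μ̄ = 0.4, so λ = 22 × (0.16 + 0 + 0.16) = 7.04 and power is again 64%.

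The F test cannot tell these apart. In the first, zirconia lies midway between the new crowns; in the second, it lies at one end. For a question about comparison with zirconia, the two are very different.

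**Step 2: contrasts with zirconia.** For each new crown, t = (mean of new crown − mean of zirconia) / √(2s²/22), with s² pooled on 63 df. Two rules were simulated: Dunnett (reject if |t| > about 2.26), and unadjusted contrasts tested only after a significant ANOVA.

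| Endocrown, Bioflex (SD vs zirconia) | ANOVA significant | At least one Dunnett contrast | At least one contrast after significant ANOVA |
|---|---|---|---|
| +0.4, −0.4 | 64% | 35–36% | 45–46% |
| +0.8, +0.4 | 64% | 67% | 63% |
| +0.8, +0.8 | 77% | 80% | 77% |
| +0.8, 0 | 77% | 66% | 70% |

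In the first row, ANOVA is significant with neither Dunnett contrast significant in 29% of all trials, which is 29/64 = 45% of the significant ANOVAs. With the more liberal gated rule, about 64% − 46% = 18% of all trials still have a positive ANOVA and no contrast with zirconia.

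**Step 3: categorical illustration (assumed counts).** Successes of 22 (endocrown), 14 (Bioflex) and 18 (zirconia) out of 24 total 54 of 72, so 18 successes and 6 failures are expected per arm. χ² = 2 × (16/18) + 2 × (16/6) = 7.11 on 2 df, p = 0.029 (exact 3×2 test, p = 0.033). Fisher tests in pairs give p = 0.24 for endocrown against zirconia, 0.36 for Bioflex against zirconia and 0.017 for endocrown against Bioflex. The overall signal comes from the comparison that the aim does not ask for.

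**The case against.** Four counter-arguments have weight.

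**The trial is planned as an equivalence trial.** The sample size section speaks of standard and experimental treatments and a limit of 0.6, and the analysis section says an equivalence limit will be checked. A reader might infer that the plan has no inference against control at all; that goes too far, because this sentence is such an inference in intent. It names no pair, outcome or limit, however, so it does not supply the missing contrasts. What stands is that difference tests against zirconia would not establish equivalence either, so the repair must include confidence intervals.

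**A gate is already there.** A reader might infer that pairwise follow-up would raise the false-positive rate to about 12% per outcome. That figure is for three unadjusted pairwise tests run without a prior omnibus test, which the plan does not propose. With exactly three groups and normal data, pairwise tests run only after a significant ANOVA hold the familywise error at about 5% (5.0% with all arms equal; 4.9% for a null crown against zirconia when the other is at +0.8 SD). So the omnibus test need not be discarded.

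**The ±0.4 SD example partly reflects low power.** Both crowns truly differ from zirconia there, so the significant ANOVA is not a false positive. That is correct. The example shows only that the result does not reach the question asked. Setting 64% against the 18% power of one single Dunnett contrast would not be like for like; the matching figure is at least one contrast, about 35%.

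**The categorical sentence does not mention three groups.** True. The ANOVA and Kruskal-Wallis sentence is the firmer basis. For categorical outcomes the gap is that no pair is named, in a three-arm design.

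**Conclusion.** The concern holds as an omission. The aim and the control label define two comparisons with zirconia; the difference tests as written deliver neither, and the equivalence sentence does not fill the gap. Under assumed effects of +0.4 and −0.4 SD with 22 per group, a positive ANOVA leaves neither crown separated from zirconia by Dunnett in 29% of trials. The size depends on where zirconia lies: at +0.8 and +0.4 SD the Dunnett contrasts do slightly better than ANOVA (67% against 64%).

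A stronger conclusion, that the omnibus tests must be replaced by Dunnett, is not supported. Neither follow-up rule dominates: for at least one crown against zirconia, Dunnett gives about 35% against 46% for gated contrasts at +0.4/−0.4, but 67% against 63% at +0.8/+0.4. Adding the two contrasts is needed; dropping the omnibus test is a choice.

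All percentages assume normal data and a common SD. The logical point, that an omnibus p-value does not identify the crown, needs no assumption about effect size.

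**What to change.** In Data Management and Analysis:

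1. Name endocrown minus zirconia and Bioflex minus zirconia as the two prespecified contrasts for every outcome, numeric, ranked or categorical. Report each with an estimate and 95% CI.
2. For the outcome to which the 0.6 limit applies, name that outcome and judge each CI against the limit. Report these intervals whether or not an omnibus test is significant; a gate on a difference test should not decide whether equivalence is assessed.
3. Fix one multiplicity rule for the difference p-values before data are seen: either Dunnett (Holm for rank and categorical tests), or contrasts tested only after a significant omnibus test. With three groups, both hold the error near 5% per outcome for normal data. The omnibus test may be kept.
4. Report endocrown against Bioflex as secondary or descriptive.

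The cost is analysis wording only: no added children, visits or measurements. One small downside is that Dunnett-adjusted contrasts reject less often than the omnibus test when only one crown differs (66% against 77% at 0.8 SD), although the omnibus result does not say which crown it is. The rule works within each outcome; multiplicity across outcomes and visits is a separate matter.

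### The plan names no order-respecting test for categorical data and does not say how USPHS grades and 5-point satisfaction ratings are classed; if treated as categorical, 5-level ratings lose substantial power and three-grade scores a modest amount

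*Combined protocol and SAP*

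**What the plan says.** The section Data Management and Analysis offers two routes. Numeric variables are compared by ANOVA if normally distributed; otherwise, comparisons for "non-normally distributed numeric variables will be done by Kruskal Wallis test". For everything categorical the rule is: "Categorical data will be described as numbers and percentages and comparisons will be done by chi square test or fisher exact as appropriate". No trend or ordinal method is named for categorical data, and no outcome is assigned to either route.

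Two sets of outcomes described under Observations (Clinical Performance Assessment) are ordered scores:

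- Clinical performance: "Retention, marginal adaption, fracture of the restoration were scored using a modified United States Public Health Service (USPHS) criterion". The number of grades is not given. Assessments are at 3, 6 and 12 months.
- Parent satisfaction with color, shape and size, at 12 months: "Parents' responses were rated on a 5-point Likert-type scale".

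The testing level is set by "A p-value less than or equal to 0.05 will be considered statistically significant" and "All tests will be two tailed". The Sample Size section frames the trial as equivalence on a difference in means and gives no power figure for any ordered or categorical outcome.

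**The concern.** Chi-square and Fisher tests give the same p-value however the category labels are shuffled. A crown whose ratings drift consistently downward gets no credit for that consistency, and the group effect is spread over more degrees of freedom than a rank test needs.

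Clinical performance and parent satisfaction are both in the trial's title. The trial expects no difference between crowns, so an insensitive test errs towards the expected answer: a real deficit in marginal adaptation or satisfaction is more likely to come out as not significant. Because the class of each score is left open, the analyst could also choose the route after seeing the data.

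**Working it through.** **1. The plan's own figure.** The only stated size is this: "then 22 patients in each group are required to be 80% sure that the limits of a two-sided 95% confidence interval will exclude". The margin is 0.6 on the scale of group means. For equivalence of two means with true difference zero,

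n = 2 × SD² × (z₀.₉₇₅ + z₀.₉₀)² / 0.6² = 2 × (1.960 + 1.282)² × (SD/0.6)² ≈ 21.0 × (SD/0.6)².

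The SD is not stated, so 22 cannot be reproduced from the document alone. An assumed SD of 0.60 to 0.61 gives 21.0 to 21.7, which rounds up to 22. This figure says nothing about power for ordered scores, so that has to be simulated.

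**2. Degrees of freedom.** With three groups and k levels, chi-square has (3−1)(k−1) degrees of freedom and Kruskal-Wallis has 2.

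| Levels | Chi-square | Kruskal-Wallis |
|---|---|---|
| 5 | 8 | 2 |
| 3 | 4 | 2 |
| 2 | 2 | 2 |

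Any loss should therefore be largest for five levels and vanish for two.

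**3. Simulation inputs.** From the document: three groups, 22 per group (before the increase to 24 for losses), two-sided 0.05. Assumed, because the document gives none: the baseline distributions (listed best to worst) and a common odds ratio (OR) making one crown worse. For example, a top-grade share of 0.80 has odds 4; dividing by OR 4 gives odds 1, a share of 0.50. The same division at 0.95 cumulative gives 19/4 = 4.75, or 0.83. So 0.80/0.15/0.05 becomes about 0.50/0.33/0.17.

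There were 4000 runs per scenario, so the Monte Carlo standard error is at most √(0.25/4000) ≈ 0.8 points.

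**4. Power, Pearson chi-square vs Kruskal-Wallis.**

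| Score and baseline | OR | Chi-square | Kruskal-Wallis |
|---|---|---|---|
| 5 levels, three baselines | 2 | 10–13% | 23% |
| 5 levels, three baselines | 3 | 27–31% | 50–53% |
| 5 levels, three baselines | 4 | 44–46% | 72–73% |
| 5 levels, three baselines | 6 | 70–71% | 91–92% |
| 3 grades, 0.60/0.30/0.10 | 4 | 59% | 69% |
| 3 grades, 0.80/0.15/0.05 | 4 | 48% | 61% |
| 3 grades, 0.90/0.08/0.02 | 4 | 32% | 43% |
| 3 grades, 0.95/0.04/0.01 | 2 | 5% | 7% |
| 3 grades, 0.95/0.04/0.01 | 4 | 18% | 26% |
| 2 levels, 0.90/0.10 | 4 | 45% | 44% |

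The five-level baselines were 0.50/0.30/0.12/0.05/0.03, five equal shares of 0.20, and 0.35/0.35/0.20/0.07/0.03. Within each baseline the loss at OR 3 to 6 runs from about 20 points (71.3% vs 91.0%) to 28 points (44.2% vs 72.2%). Across the three-grade scenarios it runs from about 2 points (4.5% vs 6.6%) to 13 points (48.2% vs 61.0%).

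**5. Does the Fisher option restore the power?** Not for five levels. The Fisher-Freeman-Halton exact test (600 runs) gives 47–49% at OR 4, against 72–74% for a permutation Kruskal-Wallis. For three grades at 0.80/0.15/0.05 and OR 4 it gives 52% vs 63%. Where defects are rare the gap narrows: 20% vs 23% at 0.95/0.04/0.01 and OR 4.

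**6. Type I error.** With no true difference, Kruskal-Wallis rejected in at most 5.4% of runs, so its extra power is not bought with false positives.

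**7. Where the rank test does worse.** With two crowns at 70/28/2 and one at 70/5/25 (same share of top grades, many more outright failures), chi-square has 82% power and Kruskal-Wallis 7%. With satisfaction polarised (5/10/20/35/30 against 25/5/5/10/55), the figures are 76% and 9%. Both are deliberately extreme, with 3000 runs each.

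**The case against.** The strongest reply is that the plan never calls these scores categorical. The USPHS items are described as scored, and the sample size rests on a difference in means, which fits numeric handling. If the scores are numeric and non-normal, Kruskal-Wallis already applies. This stands in part. A reader might infer that the plan sends USPHS grades to chi-square as a matter of record; the document does not say so. It remains the natural reading for clinical grades and a possible one for satisfaction, and nothing in the plan rules it out.

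Second, the large loss belongs to the five-level ratings, the less certain case. This also stands. A reader might infer that much of the power is lost for every ordered outcome. With three grades the loss is modest, and when nearly all teeth get the top grade, low event counts limit power more than the choice of test does.

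Third, sparse cells might look like a separate defect: even 72 molars over a 3 × 5 table average only 72/15 = 4.8 per cell. The Fisher option already answers that as a matter of validity, though not of ordering.

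Fourth, a proportional-odds shift is the pattern rank tests detect best, and the non-monotone examples show a real trade-off. So a switch to ranks is not free of downside, and grade counts should still be shown.

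**Conclusion.** The point holds in a limited form. The class of each ordered score is unstated, and the only tests named for categorical data ignore order. If that route is taken, the cost at 22 per group is roughly 20 to 28 points of power for five-level ratings at odds ratios of 3 to 6, about 2 to 13 points for three-grade USPHS scores, and none for two-level scores. These sizes rest on assumed distributions and a one-directional shift in one crown; the document supplies neither, nor the number of USPHS grades.

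A reader might also infer that a better test would make a non-significant result support equal performance. It would not. Equivalence needs a confidence interval set against a margin, and the plan's only stated margin is for a difference in means on an unnamed outcome. The gain here is fewer missed deficits, at almost no cost, which makes the change worth making.

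**What to change.** State the data type and number of levels of each outcome, and amend the categorical-data sentence along these lines:

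> Ordered scores with three or more levels (satisfaction with color, shape and size; USPHS retention, marginal adaptation and fracture where graded in three or more levels) will be compared by the Kruskal-Wallis test, with A vs C and B vs C contrasts adjusted for multiplicity. Binary and unordered variables will be compared by chi-square or Fisher's exact test. Counts and percentages per grade will be tabulated by group for all scores.

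A proportional-odds model reporting an odds ratio with 95% CI is an acceptable alternative to the rank test; choose one in advance.

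The multiplicity rule should be named. Three USPHS items at three visits plus three satisfaction items (if rated separately) make 3 × 3 + 3 = 12 overall comparisons, each with two contrasts.

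The cost is a sentence or two, with no extra patients or data. The downside is that a rank test can miss a non-monotone difference, such as more outright failures with the same share of top grades; the tabulated grades would show it.
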